
# 2.5 Study Design

- The primary purpose for this study is treatment. The protocol is designed to evaluate one or more interventions for treating a disease, syndrome, or condition.
- The interventional model is Sequential.
- The number of intervention arms is up to 3.
- The study will be not be masked (not blinded).
- The study will be not be randomized.

This is a phase 1b study evaluating the safety and tolerability of infigratinib. Cohort 1 will utilize the combination of tamoxifen and infigratinib. We anticipate that this combination may play a role in the future development of infigratinib for hormone receptor-positive breast cancer, necessitating the establishment of their safety. For example, tamoxifen and infigratinib might be used in the early-stage, (neo)adjuvant setting as well as the late-stage, metastatic setting.

In Cohort 1, up to 3 dose levels of infigratinib may be evaluated (125 mg; 100 mg; and 75 mg) in combination with tamoxifen. This pilot study is a necessary step for the future development of infigratinib in combination with tamoxifen and will serve as a safety run-in evaluation for a follow-up study. For this cohort, a 3 + 3 design will be employed starting at 100 mg, and allowing subjects who start at 100 mg to escalate to 125 mg (see Section 12.4).

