#### 6. DOSE MODIFICATIONS

Individually, each subject will be allowed up to dose-reduce to 75 mg infigratinib, as follows (see also Table 5).

- If a subject's infigratinib dose is 125 mg, 2 dose reductions of infigratinib are permitted.
- If a subject's infigratinib dose is 100 mg, 1 dose reduction of infigratinib is permitted.
- If a subject's infigratinib dose is 75 mg, no dose reduction of infigratinib is permitted, with infigratinib treatment discontinuation the only option.

Subjects should discontinue infigratinib if toxicities persist following dose reductions to the lowest level allowed, unless it has been discussed and approved by the QED Therapeutics' Medical Monitor.

Following resolution of toxicity to baseline or  $\leq$  Grade 1, or  $\leq$  Grade 2 for hematologic toxicities, treatment is resumed at either the same or lower dose of study drug as per the criteria in Table 6. Adverse event lab abnormalities outlined in Table 6 should be followed at least weekly until the specified resolution. If treatment is resumed at the same dose of study drug, and the same toxicity recurs with the same or worse severity regardless of duration, dose must be reduced to the next lower dose level. If treatment is resumed at the lower dose of study drug, and the same toxicity recurs with the same or worse severity, the subject should have a second dose reduction.

Subjects who are withdrawn from the study for a study related AE or an abnormal laboratory value must be followed as described in Section 7.3.

**Table 5.** Dose Modification Scheme for Infigratinib

Dose Reduction			
	Dose level 3	(Starting) Dose level 2	Dose level 1
Infigratinib	125 mg	100 mg	75 mg

In exceptional situations, study drug may continue even if the subject experienced one of the treatment stopping rules. The decision to allow for continuation of treatment will be made on a case-by-case basis following discussion between QED Therapeutics and the investigator.

**Table 6.** Criteria for Interruption and Re-initiation of Infigratinib for AEs Considered to be Possibly Related to Infigratinib

Worst Toxicity CTCAE (v5.0) Grade (Unless Otherwise Specified)	Recommended Dose Modifications any Time During a Cycle of Therapy					
CARDIAC DISORDERS						
Cardiac - Prolonged QTcF Interv	Cardiac - Prolonged QTcF Interval					

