Grade 2 (≥ 2.00 to 3.0 × ULN or 2.0 to 3.0 × baseline)	
 
Hold dose of infigratinib until resolved to Grade ≤ 1 or baseline
 
If resolved within ≤ 7 days, maintain dose level of infigratinib
 
If resolved between > 7 days and 14 days, decrease by 1 dose level of infigratinib
 
If not resolved within ≤ 14 days, discontinue infigratinib
 
					
Grade ≥ 3 (> 3.0 × ULN or > 3 × baseline)	Discontinue infigratinib					
	INVESTIGATIONS – HEPATIC					
AST or ALT						
Grade 3 (> 5.0 to 20.0 × ULN) without bilirubin elevation > 2.0 × ULN	Hold dose of infigratinib until resolved to CTCAE Grade ≤ 1 or baseline  • If resolved within ≤ 7 days, decrease by 1 dose level of infigratinib  • If not resolved within ≤ 7 days, discontinue infigratinib					
Grade 4 (> 20.0 × ULN) without bilirubin elevation > 2.0 × ULN	Discontinue infigratinib					
AST or ALT and Bilirubin						
AST or ALT > 3.0 to 5.0 × ULN and total bilirubin > 2.0 × ULN without liver metastasis or evidence of disease progression in the liver	
 
Hold dose of infigratinib until both transaminases and bilirubin resolved to CTCAE Grade ≤ 1 or baseline.
 
If resolved within ≤ 7 days, decrease by 1 dose level of infigratinib.
 
If not resolved within ≤ 7 days, discontinue infigratinib
 
					
AST or ALT > 5.0 × ULN and total bilirubin > 2.0 × ULN	Discontinue infigratinib					

**Table 6.** Criteria for Interruption and Re-initiation of Infigratinib for AEs Considered to be Possibly Related to Infigratinib

Worst Toxicity CTCAE (v5.0) Grade (Unless Otherwise Specified)	Recommended Dose Modifications any Time During a Cycle of Therapy						
LABORATORY / METABOLIC DISORDERS							
Asymptomatic Amylase and/or I	ipase Elevation						
present, consider a CT scan or oth	nptoms of acute pancreatitis (abdominal pain or tenderness), and, if er imaging study to assess the pancreas, liver, and gallbladder to creatitis and assess for complications.						
Grade 3 (> 2.0 to 5.0 × ULN)	Hold dose of infigratinib until resolved to CTCAE Grade ≤ 2						
	decrease by 1 dose level of infigratinib						
	
 
If not resolved within ≤ 14 days, discontinue infigratinib
 
						
	For recurrent Grade 3 asymptomatic lipase or amylase elevation despite dose reduction, infigratinib should be held and continuation of therapy should be discussed with the medical monitor following resolution to ≤ Grade 2.						

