Grade 4 (> 5.0 × ULN)	For any Grade 4 asymptomatic lipase or amylase elevation, infigratinib should be held and continuation of therapy should be discussed with the medical monitor following resolution to ≤ Grade 2.						
Hyperphosphatemia							
Serum phosphorus > 5.5 to 7.0 mg/dL	Maintain dose level of infigratinib and optimize phosphate lowering therapy (see "Management of Hyperphosphatemia" in Section 4.2).						
Serum phosphorus > 7.0 mg/dL	If serum phosphorus is > 7.0 mg/dL, serum phosphorus should be monitored every 2 to 3 days until ≤ 7.0 mg/dL.						
	For serum phosphorus that is > 7.0 mg/dL for more than 7 days, or for a single serum phosphorus > 9.0 mg/dL:						
	
 
Hold infigratinib dose until resolved to serum phosphorus ≤ 5.5 mg/dL.
 
						
	For serum phosphorus that is > 7.0 mg/dL for more than 7 days:						
	
 
Restart infigratinib at the same dose level with increased phosphate binder dosing if the subject did not receive maximal phosphate binder dosing (sevelamer 1600 mg 3 times daily).
 
						
	
 
Reduce one dose level of infigratinib if the subject had received maximal phosphate lowering therapy (sevelamer 1600 mg three times daily). Continue maximal phosphate binder dosing.
 
						
	For serum phosphorus that is > 9.0 mg/dL:						
	
 
Reduce one dose level of infigratinib. Restart infigratinib with maximal phosphate binder dosing.
 
						
	It is recommended that phosphate binder dosing continues during infigratinib dose interruptions for hyperphosphatemia.						

**Table 6.** Criteria for Interruption and Re-initiation of Infigratinib for AEs Considered to be Possibly Related to Infigratinib

Worst Toxicity CTCAE (v5.0) Grade (Unless Otherwise Specified)	Recommended Dose Modifications any Time During a Cycle of Therapy
Hypercalcemia	
Serum calcium Grade 2	
 
Hold infigratinib dose until resolved to Grade 1 or baseline:
 
If resolved within ≤ 7 days after suspending infigratinib, maintain dose level
 
If resolved between > 7 days and 14 days after suspending infigratinib, decrease by 1 dose level
 

	If not resolved within ≤ 14 days, discontinue infigratinib
Serum calcium ≥ Grade 3	Discontinue subject from study drug
	NERVOUS SYSTEM DISORDERS
Any Grade 2 neurotoxicity	Omit dose of infigratinib until resolved to CTCAE Grade ≤ 1, then decrease by 1 dose level of infigratinib  • If not resolved within ≤ 14 days, discontinue infigratinib

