#### 10. MEASUREMENTS

### 10.1 Primary endpoint:

The primary endpoint is the incidence of dose-limiting toxicities (DLTs) in the first 2 cycles of therapy at a specific dose. In Cohort 1, in a subset of subjects who start at infigratinib 100 mg and complete 2 cycles with no DLTs and who remain on study for Cycles 3 and 4, the dose of infigratinib will be increased to 125 mg starting with Cycle 3 and the number of DLTs in Cycles 3 and 4 will be counted toward the primary endpoint (for the 125 mg dose), in addition to the number of DLTs in Cycles 1 and 2 (for the 100 mg dose). For all other subjects, the primary endpoint will be the number of DLTs in Cycles 1 and 2.

DLTs will be graded using NCI CTCAE (Common Terminology Criteria for Adverse Events), v5.0. DLTs will be defined as an adverse event (AE) or abnormal laboratory value at least possibly related to therapy with infigratinib including those AEs and abnormal laboratory values that result in a failure to meet the criteria for re-treatment. The criteria for defining a DLT, which are pre-specified based on the pre-clinical toxicity of infigratinib, are listed in Table 7.

Individual subjects who had a DLT may be retreated, after recovery, at the next lowest dose level.

Investigators will notify QED Therapeutics within 7 days of any DLTs observed.

**Table 7.** Criteria for defining dose-limiting toxicities

TOXICITY	DLT CRITERION
Skipped/ delayed dose	The inability to administer infigratinib on ≥ 75% of scheduled treatment days during cycle 1 at that dose (ie, ≥ 16 days of the 21 days of planned treatment) due to unresolved adverse event of any grade and considered at least possibly, probably, or definitely related to the study drug.
	Delay in 2 nd cycle administration at that dose due to failure of recovery from a possibly, probably, or definitely related adverse event to Grade ≤ 1 or baseline by Day 43 (Day 28 of Cycle 1 + 15 days), except for alopecia.
Blood/ bone marrow	Neutropenia     • Febrile, CTCAE Grade ≥ 3.     • CTCAE Grade ≥ 3 for > 7 consecutive days
	Thrombocytopenia
	Anemia CTCAE Grade 4
Renal/ genitourinary	Creatinine:  • CTCAE Grade 1 for > 7 consecutive days and serum inorganic phosphorus  > 5.5 mg/dL and/or serum total calcium x serum inorganic phosphorus  > 55 mg²/dL² and despite phosphorus lowering therapy for ≥ 14 days
	
 
CTCAE Grade 2 for > 7 consecutive days
 
CTCAE Grade ≥ 3
 

**Table 7.** Criteria for defining dose-limiting toxicities

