### 10.3.1 Primary Outcome

**Primary Outcome Title**: Dose-limiting Toxicity (DLT)

**Primary Outcome Measure Description**: The primary outcome for this study is dose-limiting toxicities (DLTs) during the first 2 cycles of therapy at a specific dose. All grades per the Common Terminology Criteria for Adverse Events (CTCAE). DLT is defined as a related and clinically-significant adverse event (AE), including missed doses due to a related AE. Due to limited number of characters that can present in this field, it is not possible to consistently provide additional details across all sub-elements of this outcome. See protocol. The outcome is expressed as the number of DLT events by the assigned infigratinib dose level, a number without dispersion.

Time Frame: 8 weeks.

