# 12.4 Primary Safety Analysis

Cohort 1 (infigratinib plus tamoxifen) will follow the 3+3 design evaluating 3 infigratinib doses levels, starting at 100 mg infigratinib 3 weeks on/1 week off) and moving to, if needed, 75 mg or 125 mg infigratinib 3 weeks on/1 week off. Given the nature of this cohort to be a safety run-in and the limited number of available subjects for this population, intra-subject dose-escalation will be allowed. The risk with intra-subject dose-escalation is that a dose may be declared overly toxic when the toxicities should be attributed to the number of cycles rather than the dose, but it is believed this is a conservative approach focused on subject safety.

Initially, 3 subjects will be treated at 100 mg for 2 cycles. If there are no DLTs observed in a subject at 100 mg after 2 cycles, the subject will escalate to 125 mg for 2 additional cycles. If 1 DLT is observed at 100 mg, an additional 3 subjects will be treated at 100 mg. If 2 or more DLTs are observed at 100 mg, an additional 3 subjects will be treated at 75 mg. If 1 DLT is observed at 75 mg, an additional 3 subjects will be treated at 75 mg. If no DLTs are observed in the first 3 subjects at 100 mg, but 1 DLT is observed at 125 mg, an additional 3 subjects will be treated at 125 mg, an additional 3 subjects will be treated at 125 mg. If 2 or more DLTs are observed at 125 mg, Cohort 1 will close. If a dose achieves no DLTs in 3 subjects after 2 cycles or 1 DLT in 6 subjects after 2 cycles, that dose will be declared safe for use in the main phase 2 trial.

If a subject withdraws prior to the completion of the first 2 cycles of therapy without having experienced a DLT, an additional subject will be enrolled at that dose level.

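### Sections 10.1 and 12.4 do not say how to treat a 100 mg starter cut to 75 mg without a DLT; read literally, the subject goes to 125 mg and counts as DLT-free at 100 mg.

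*Combined protocol and SAP*

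**What the plan says.** Section 10.1 identifies the subjects to be escalated as "subjects who start at infigratinib 100 mg and complete 2 cycles with no DLTs and who remain on study for Cycles 3 and 4" and states that "the dose of infigratinib will be increased to 125 mg starting with Cycle 3". Section 12.4 puts it per subject: "If there are no DLTs observed in a subject at 100 mg after 2 cycles, the subject will escalate to 125 mg". Section 2.5 is softer and speaks of "allowing subjects who start at 100 mg to escalate to 125 mg".

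Section 6 permits one reduction from 100 mg, to 75 mg. Table 6, whose column heading calls its entries recommendations and applies them at any time in a cycle, lists the triggers. For Grade 3 AST/ALT it says "If resolved within ≤ 7 days, decrease by 1 dose level of infigratinib"; for Grade 2 neurotoxicity, "Omit dose of infigratinib until resolved to CTCAE Grade ≤ 1, then decrease by 1 dose level of infigratinib". After a toxicity resolves, "treatment is resumed at either the same or lower dose of study drug as per the criteria in Table 6". Section 6 does not say whether a reduced subject may later go up.

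Under Section 12.4 a dose is declared safe on no DLTs in 3 subjects or 1 in 6. Only a subject who withdraws within the first two cycles without a DLT leads to an additional enrolment. Dose reduction is not itself a Table 7 criterion, and no minimum exposure at the assigned dose is stated.

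**The concern.** The escalation conditions in Section 10.1 are the starting dose, two completed cycles, no DLT and remaining on study. The dose being taken at the end of Cycle 2 is not among them. If Table 6 can lower that dose for an event that is not a DLT, the same subject can meet every escalation condition while taking 75 mg.

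Two things are then at stake. A site reaching Cycle 3 Day 1 with such a subject has wording that directs 125 mg, two levels above the current dose, and a dose-modification section that describes only staying level or going down. Section 10.1 itself has a subject with a DLT retreated, if at all, at the next lower level. And the count behind the primary decision takes in, as a DLT-free result at 100 mg, someone who spent part of the window at 75 mg because of drug-related toxicity.

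**Working it through.** **1. The plan's own figure.** The synopsis gives 3 to 12 evaluable subjects. Following Section 12.4 and counting new enrolments only:
- Minimum: 0 of 3 at 100 mg, the same three escalate, and no further subjects are needed = 3.
- Maximum: 3 + 3 at 100 mg with at least two DLTs in all, then 3 + 3 at 75 mg = 12.

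Both ends reproduce. At the minimum, the same three subjects decide 100 mg and 125 mg.

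**2. Reductions that are not DLTs.** Table 6 set against Table 7:

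| Event | Table 6 | Table 7 threshold |
|---|---|---|
| Grade 2 neurotoxicity | one level down | no row; the catch-all starts at Grade 3 |
| Grade 2 vomiting, uncontrolled | one level down | Grade 3 or 4 |
| Recurrent Grade 2 diarrhea | one level down | Grade 3 or 4 |
| Grade 2 central serous retinopathy, resolved within 14 days | one level down | ocular Grade 3 or above |
| Grade 3 asymptomatic lipase/amylase, reversing within 7 days | one level down | not reversed within 7 days |
| Grade 3 AST/ALT, resolved within 7 days | one level down | more than 7 days, but above 8 x ULN at any duration with hepatic metastases |
| Afebrile Grade 4 neutropenia, 7 days or less | one level down | more than 7 days |

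The AST/ALT entry is therefore outside Table 7 only below the hepatic-metastases threshold. The thrombocytopenia criterion cannot be read in the available text and is not used.

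**3. What the skipped-dose row of Table 7 catches.** It requires at least 16 of 21 days given in Cycle 1 (16/21 = 76%; 15/21 = 71%). Six days missed for an unresolved related event of any grade is a DLT. A hold from Day 15 to the end of dosing leaves 14/21 = 67%, also a DLT. It does not catch:
- holds of five days or fewer (21 - 5 = 16);
- a hold starting on Day 17 or later, when 16 days have already been given;
- anything in Cycle 2, since the row covers Cycle 1 only.

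**4. One subject followed through.** The subject starts at 100 mg, has Grade 2 neurotoxicity in Cycle 2, is held, and resumes at 75 mg. No Table 7 row is met. The subject has not withdrawn, so no additional subject is enrolled. On the literal wording the subject is one of the DLT-free three at 100 mg and goes to 125 mg. The step is 125/75 = 1.67, an increase of 67%.

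**5. How often.** The documents give no rate of non-DLT reductions in Cycles 1-2. Let q be that rate; 5% to 10% is an assumption. The chance of at least one among the first three subjects is 1 - (1 - q)^3:
- q = 5%: 1 - 0.95^3 = 0.143
- q = 10%: 1 - 0.90^3 = 0.271

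**6. How much classification matters (illustration).** Take a DLT probability of 1/6 at 100 mg, the single-agent result in Section 2.2.9 (1 of 6), assumed to carry over to the combination and this two-cycle window. P(declared safe) = P(0/3) + P(1/3) x P(0/3) = 0.579 + 0.347 x 0.579 = 0.78. As an extreme contrast, let every non-DLT reduction weigh against the dose like a DLT, so that the probability becomes 1/6 + q:
- q = 5%: 0.481 + 0.399 x 0.481 = 0.67
- q = 10%: 0.394 + 0.430 x 0.394 = 0.56

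This is not the rule proposed below. It shows only that the finding at 100 mg depends on a classification the plan leaves open.

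**The case against.** The strongest reply is that the plan can be read so that the problem does not arise. Section 12.4 speaks of treating subjects at 100 mg for two cycles and conditions escalation on no DLT at 100 mg after two cycles; Section 10.1 ties the endpoint to a specific dose. On that reading a subject cut to 75 mg has not completed the window and does not qualify. Section 2.5 and the opening of Section 12.4 are permissive, and Table 6 is headed as recommendations. This stands as an available reading. But the operative sentences say the dose will rise, Section 10.1 selects on the starting dose, and no evaluability rule states the exception.

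Several stronger readings are tempting and are not supported:
- A reader might infer that Section 6 forbids what Section 10.1 orders. It does not: its sentence governs resumption after a toxicity and is silent on later escalation.
- A reader might infer that every 100 mg starter without a DLT goes up. Section 10.1 limits this to those who complete two cycles and remain on study.
- A reader might infer that the skipped-dose row never helps. It catches many Cycle 1 cases, and more still if its reference to the dose is taken to mean days given at 100 mg.
- A reader might rely on Section 10.3.1, which reports the "number of DLT events by the assigned infigratinib dose level". That is the registry description and weak evidence of how Section 12.4 counts subjects.

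**Conclusion.** The point holds as a gap with a concrete consequence. Sections 10.1 and 12.4 do not expressly require a subject to be on 100 mg when escalated or when counted, and Table 6 produces subjects who are not. Read literally, such a subject is directed from 75 to 125 mg and is a third of the evidence when a dose is judged on three subjects. The firm part is short holds, late Cycle 1 events and Cycle 2 reductions.

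The 14% to 27% rests on the assumed 5% to 10% and on independence between subjects. A reader might take it as the chance of a wrong dose decision; it is only the chance that the situation arises. A reader might also infer that both dose decisions are biased, 100 mg towards looking safe and 125 mg towards looking toxic. Those directions are plausible, but the documents give nothing from which to measure them.

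**What to change.** 1. Reconcile Sections 10.1 and 12.4 with Section 6 and Table 6, so that a site has one instruction at Cycle 3 Day 1 for a subject reduced during Cycles 1-2. Which instruction is a clinical choice for the sponsor.
2. Amend Section 12.4 so that a subject reduced within the two-cycle window without a DLT is not counted as a DLT-free completer at the starting dose, towards either 0 of 3 or 1 of 6.
3. Report these subjects separately, with the reason and the dose received by cycle, and present them with the dose decision at 100 mg and at 125 mg. They should not simply be replaced and set aside: the reduction is itself evidence of drug-related intolerance, and dropping it would make 100 mg look safer than it was.

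The cost is wording in three sections and possibly one or two more subjects to complete a dose level. Expected enrolment for three countable subjects is 3/(1 - q), or 3.2 at q = 5% and 3.3 at q = 10%; for six it is 6.3 and 6.7. These fall outside the stated 12, which already excludes replacements.
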